5.6. Statistical analysis**5.6.1. Brief summary of the analysis method (for publication)**

For the primary analysis, propensity scores will be used to match new users of the target exposure (DOAC) to new users of the comparator exposure (VKAs), to control for confounding. For the secondary analysis, propensity scores will be used to match new users of the individual target exposures to the comparator exposure (VKAs). For all analyses, cause-specific Cox proportional hazards models will be used to estimate the relative hazard ratio of ILD after exposure. Finally, meta-analysis methods will be used to synthesise results across databases.

5.6.2. Main statistical methods

Propensity score matching will be performed using a 1:1 matching of warfarin users to DOAC users using a caliper width of 0.2 of the standard deviation of the logit of the propensity score. [11] We will include the baseline risk factors and calendar year as predictor variables in the propensity score. Matching will occur by indication (AF and VTE). Absolute standardised mean differences (SMD) for each variable will be calculated before and after propensity score matching, with SMD of less than 0.1 representing successful matching. We will visually check the distributions of the propensity scores across treatment arms, within strata (indication, database). If the sample size appears insufficient after matching, we will use Inverse Probability Treatment Weighting (IPTW) instead of matching.

In the propensity-matched cohort, the incidence of each study outcome will be estimated between target (DOAC) and comparator (warfarin) groups. Cox models will be used to calculate hazard ratios for the instantaneous risk of the ILD outcome. Where death is available in the data source, competing

mortality risk will be accounted for by estimating cause-specific hazard functions. We will apply two analytical approaches: an **on-treatment analysis** (OT) and an **intention to treat analysis** (ITT as per the study by Chan et al.).

Summary of key analysis factors:

- 4 Countries
- 4 DOACs + 1x all DOACS = 5 (warfarin is comparator)
- 2 indications

This brings the number of analyses to $4 * 5 * 2 = 40$ (this number will vary depending on the analytical approach and principal findings).

5.6.3. **Meta-analysis**

Hazard ratios will be reported for each database, exposure and indication separately. Log hazard ratios will also be meta-analysed across databases using a random-effects model using REML (Restricted Maximum Likelihood). 95% Confidence intervals will be provided using the HKSJ method. [12, 13] 95% approximate prediction intervals will be provided. [14] I^2 will be estimated to describe the percentage of the variability in effect estimates that is due to heterogeneity rather than sampling error.

5.6.4. **Missing data**

The analysis will be conducted on the assumption that an individual has a condition or prescription exposure if it is recorded in their electronic health record. No multiple imputation methods will be performed. Therefore, patients with missing records for an indication will be excluded from the analyses.

5.6.5. **Sample size**

The sample size will be driven by the availability of individuals with exposures and outcomes within each database and no a priori sample size requirement will be stipulated.

5.6.6. **Sensitivity analysis**

If we observe imbalances in propensity score distributions among the cohorts after matching that includes calendar year in the model, we will examine whether undertaking calendar time stratified propensity score matching results in improvement for example by undertaking the propensity score matching within calendar year(s) (such as 2010 to 2014 and 2015 to 2019).

5.7. **Quality control**

The study will be conducted according to the ENCePP code of conduct (European Medicines Agency 2018).

Standard operating procedures or internal process guidance will be adhered to for the conduct of the study. These procedures include rules for secure and confidential data storage, quality-control procedures for all aspects of the study from protocol development to the reporting of the results.

All documents will undergo at least one round a review by an experienced reviewer, while the results from the statistical analysis will be either reviewed or checked via double coding.

The quality control of the data is the responsibility of the data holder.

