5.4. Study period

The study observation period to identify new users will be from 1st of January 2010, to 31st of December 2019 (i.e., the period before COVID-19 cases emerged).

Cohort entry will be the date of anticoagulant initiation (**index date**). New anticoagulant use will be defined as no prescription for any anticoagulant of interest in the 365 days prior to cohort entry.

Cohort exit will be the earliest of ILD, death (for databases where death is captured), end of individual observability (deregistration or end of practices contributing data where these data are captured), treatment switching (for the on-treatment analysis) or end of the study period (31st December 2019). For the analysis of any DOAC vs VKA, switching to a different DOAC will not be considered a switch of exposure.

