5.5. Variables

Outcome:

The outcome of interest will consist of an incident diagnosis of ILD. ILD consists of a heterogeneous group of conditions. The ILD phenotype is therefore a composite of different codes representing ILD in general, or as specific conditions that are classed as an ILD. Exclusion of patients with pre-existing ILD will be evaluated using a composite phenotype consisting of any ILD related code. For the outcome in the analysis, a narrower definition of ILD will be used, namely pulmonary fibrosis, pneumonitis, ILD specific codes, and drug induced ILD (please see Appendix for exemplar codes lists). As codes for drug induced ILD are infrequently used, inclusion of this as a specific subgroup may provide limited information. We followed the "narrow" scope list of terms (i.e., very specific preferred terms) documented in the Introductory Guide for Standardised MedDRA Queries (SMQs) Version 25.0 [8]. We mapped these SMQ codes to SNOMED codes and used their OMOP concept IDs, and subsequently removed any codes that indicate another well-defined cause of ILD. Detailed list of codes included are shown in **Annex 2**.

Exposure:

Exposures of interest will consist of VKAs (comparator, consisting of either warfarin, acenocoumarol, phenindione, or phenprocoumon), and DOACs (target, consisting of apixaban, dabigatran, edoxaban and rivaroxaban). Exposures will be identified through prescriptions recorded in the electronic health record. Target exposures will be evaluated by class (any DOAC (direct oral anticoagulants)) and as individual drug substances.

For the on-treatment analysis, patients will be considered continuously exposed from cohort entry (index date) up to 30 days after the date of the last anticoagulant prescription in the patients record. In order to account for different treatment episodes over time, gaps of >90 days between anticoagulant prescriptions will be considered as different treatment episodes and continuous exposure will be censored 30 days after the last prescription before the gap. Detailed list of codes and terms included to identify exposure to DOACs are shown in **Annex 2**.

Other variables:

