Baseline risk factors for ILD will be measured including: age, sex, history of pneumonia, chronic obstructive pulmonary disease, chronic kidney disease, hepatitis C, history of tuberculosis sarcoidosis, history of autoimmune diseases, history of connective tissue disorders, history of sarcoidosis, history of cancer, exposure to medications (nitrofurantoin, sulfonamides, amiodarone, methotrexate, cyclophosphamide, dronedarone, SSRIs/SNRI antidepressants, anticonvulsants, antiplatelets, statins, angiotensin converting enzyme inhibitors (ACEI), angiotensin-II receptor blockers (ARB), thiazide diuretics and systemic fluoroquinolone antibiotics [Detailed list is shown in Annex 2]), smoking status. [9, 10] Smoking status may be missing. We will include current smoking status as a binary variable. An individual will be classed as a current smoker (1) or non-current smoker (0, i.e., other smoking status or the absence of a smoking status) based on the most recent smoking status prior to their index date. Risk factors that will not be reliably identifiable include environment and occupational exposures, family history, and biologics, and will not be considered in the analysis. Information on prior radiotherapy and chemotherapy may not be available for some patients but will be included in the analysis when available.

Additionally, the incidence of ILD has changed substantially over time as well as the prescription patterns of the exposures. We will therefore also account for calendar year in the propensity score analysis.

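### VKA comparators are drawn from 2010 for every contrast; for a DOAC first recorded later, the earlier VKA initiators widen the caliper and can be matched to its users

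*Protocol*

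**What the plan says.** Section 5.4 defines a single accrual window: "The study observation period to identify new users will be from 1st of January 2010, to 31st of December 2019". No drug has its own start date.

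Section 5.5 sets five contrasts against VKA: "Target exposures will be evaluated by class (any DOAC (direct oral anticoagulants)) and as individual drug substances". Section 5.6.1 makes the class contrast primary and the four individual drugs secondary.

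Section 5.6.2 pairs comparator and DOAC users one to one, within indication, and fixes how far apart a pair may lie: "using a caliper width of 0.2 of the standard deviation of the logit of the propensity score". Calendar time enters only through the score: "We will include the baseline risk factors and calendar year as predictor variables in the propensity score". The protocol does not say in which patients the standard deviation is taken, so on its face this is the whole pool of the contrast.

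The reason for including year is in 5.5, which says that both ILD incidence and prescribing have changed substantially over time, and continues: "We will therefore also account for calendar year in the propensity score analysis".

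There are two safeguards. Section 5.6.2 calls for standardised mean differences (SMDs) before and after matching, with less than 0.1 as success, and for a visual check of score distributions. Section 5.6.6 adds a sensitivity analysis, matching within calendar periods (2010-2014 and 2015-2019 are the example), under this condition: "If we observe imbalances in propensity score distributions among the cohorts after matching that includes calendar year in the model".

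**The concern.** A VKA initiator in a year when a given DOAC was not yet in use had no chance of receiving that DOAC, so such patients carry no valid information for that contrast. Two things can follow.

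- Their very low scores spread the distribution of the logit. The caliper is a fixed multiple of that spread, so it widens for everyone, including patients in the overlapping years.
- If year is modelled as a linear term, their scores are low but finite. Some can then be paired with DOAC users who entered years later, although the protocol itself says that ILD incidence changed over those years.

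At stake is some residual confounding by calendar time and ILD risk factors. It would be greatest for a DOAC with a short period of use.

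**Working it through.** **Inputs.** From the protocol: ten entry years (2010-2019), 1:1 matching within indication, caliper 0.2 SD of the logit score, year as a predictor, SMD limit 0.1. The protocol gives no first-use dates, uptake figures, event counts or SD, and it leaves the coding of year open. There is therefore no plan figure to reproduce, and everything below on size rests on assumed uptake.

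**Step 1: why the caliper widens.** The caliper is c = 0.2 × SD(logit score). Suppose that a fraction p of the patients over whom the SD is taken entered before first use, and that their mean logit lies d below that of the others. Then

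Var = (1 − p)·s₁² + p·s₀² + p(1 − p)·d²,

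where s₁² and s₀² are the variances within the later and earlier entrants. The last term grows with d². With linear year, d is finite. With one category per year, the years before first use contain no DOAC users, so unpenalised maximum likelihood drives d towards infinity. The caliper then depends on where the software stops.

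**Step 2: matching simulation.** Assumptions: 40,000 initiators spread evenly over 2010-2019, three confounders, several uptake curves, greedy nearest-neighbour matching, one seed, and logits truncated at ±16 under separation. Selected results with the pooled within-arm SD, full window against years from first use onward:

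| Uptake, first use | Year coding | Caliper, full / restricted | Ratio | Mean pair distance | Year SMD | VKA matches from before first use (full window) |
|---|---|---|---|---|---|---|
| DOAC dominant, 2010 | linear | 0.358 / 0.358 | 1.0 | 0.042 / 0.042 | 0.020 / 0.020 | 0% |
| DOAC dominant, 2012 | linear | 0.409 / 0.303 | 1.3 | 0.043 / 0.031 | 0.025 / 0.019 | 8.4% |
| Common to dominant, 2016 | linear | 0.394 / 0.177 | 2.2 | 0.020 / 0.006 | −0.050 / −0.003 | 4.6% |
| DOAC dominant, 2012 | categorical | 1.176 / 0.301 | 3.9 | 0.364 / 0.031 | 0.239 / 0.018 | 0% |
| Common to dominant, 2016 | categorical | 0.986 / 0.177 | 5.6 | 0.120 / 0.007 | 0.084 / −0.003 | 0% |

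Over all settings with first use in 2012-2016, the full-window caliper was 1.2-3.2 times wider with linear year and 3.7-7.8 times wider with categorical year, counting both definitions of the SD. With linear year, about 1-9% of matched VKA users came from before first use, and every SMD still passed (confounders at most 0.07, year at most 0.06 in absolute value). Where VKA users were plentiful (first use 2016, rare uptake), the wider caliper changed almost nothing: the 95th percentile of pair distance was 0.003 with either window.

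**Step 3: effect on the hazard ratio.** Assumptions: VKA initiators falling from 1000 to 180 per year, six confounders, true HR 1, crude HR about 1.5, 20 datasets per setting. The null HR is the ratio of mean hazards in the matched arms. With linear year:

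| Lag of first use after January 2010 | 1 year | 2 years | 3 years | 5 years |
|---|---|---|---|---|
| Full window | 1.012 | 1.021 | 1.024 | 1.037 |
| Restricted | 1.007 | 1.005 | 1.002 | 1.013 |

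With a ridge-penalised score the figures were 1.01-1.02 against 1.00-1.01. A separate simulation with lags of 1-5 years gave 1.01-1.03 against 1.00-1.01 for linear year.

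With unpenalised categorical year, the results differ between implementations: 1.03-1.07 in one and 1.09-1.13 in another, against 1.00-1.01 when restricted. Changing only the number of fitting iterations (4, 8, 15, 25; 3-year lag, 6 datasets) moved the caliper through 0.42, 0.69, 1.17 and 1.86, and the null HR through 1.03, 1.05, 1.14 and 1.28. A light ridge penalty in the same check gave 1.03.

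**Step 4: the 5.6.6 safeguard.** It is triggered by visible imbalance in the score distributions. With linear year the balance checks pass, so it would probably not be triggered. The example blocks can also straddle first use: for a DOAC first recorded in 2013, the block 2010-2014 would contain three years before use (2010, 2011, 2012). When run in the outcome simulation, those blocks gave 1.00-1.03.

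**The case against.** The strongest reply is that the premise is not in the protocol. It gives no first-use date for any DOAC, and where use is recorded from 2010 the two windows are identical. That stands. A reader might infer from the common window that every contrast is harmed, but the documents do not support this.

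A reader might also infer that the primary hazard ratio is biased. Section 5.6.1 makes the DOAC class primary, and the class starts with the earliest DOAC, so its lag is the shortest. At a 1-year lag with linear year the figures are 1.012 against 1.007, which is negligible.

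Third, a bias of 9-13% might be read off the categorical-year results. That size reflects how the software treats complete separation, as the iteration check shows. It is not a property of the protocol, which leaves the coding of year and the fitting method open, as a protocol may. In that setting the year SMD was 0.27-0.43, which the 0.1 criterion would expose. It would be wrong to say that the plan accepts such matches unnoticed.

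Finally, earlier VKA users are not unmatchable in general, and a wide caliper permits distant pairs without forcing them. Both points stand.

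What remains is narrower. The pool is unrestricted, the caliper widened in every simulated setting with late first use, and the linear-year case passes the plan's balance checks. The only calendar-time remedy is a conditional sensitivity analysis.

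**Conclusion.** The point holds as a cheap improvement. The 0.2 SD caliper is not itself an error. For any DOAC whose recorded use begins after 2010, VKA initiators from earlier years widen the caliper, and with linear year a few per cent of matched comparators come from years when that DOAC was not in use.

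The expected distortion is usually small: a null HR of about 1.01-1.04 instead of 1.00-1.01 with linear year, and little with a penalised score. It lies mainly in the secondary individual-DOAC contrasts. It is larger only with unpenalised categorical year and scarce VKA users, where no single figure can be defended and the year SMD often exceeds 0.1.

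These sizes rest on assumed first-use dates, uptake, confounder strength and greedy matching, with few datasets and no Monte Carlo error attached. Confidence in the direction is good; confidence in the size is low.

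**What to change.** In 5.4 and 5.6.2, state that for each contrast, database and indication, DOAC and VKA new users are restricted to calendar years from the first year in which that DOAC (for the class contrast, any DOAC) is recorded for that indication. Fit the propensity score and compute the SD for the caliper in that restricted set.

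The start year can be read from the data, so this is one date filter per contrast, and it changes nothing where use is recorded from 2010.

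The cost is fewer matched pairs. With linear year the outcome simulation lost 0-2%. The two late-start linear rows of the matching table lost 1.4% (5187 to 5115) and 3.2% (5053 to 4891). With categorical year the outcome simulation lost 17-25%, and the two categorical rows lost 14.0% (5950 to 5117) and 11.0% (5507 to 4901). The categorical losses are mostly poorly matched pairs.

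One limit remains: a first year with only a handful of DOAC users still holds VKA users with scores near zero, so the balance checks in 5.6.2 are still needed. Matching exactly on calendar year, which 5.6.6 already contemplates as an option, would be an alternative if made part of the main analysis.

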21 June 2023

Protocol

Title: Association between use of direct oral anticoagulants (DOACs) and increased risk of interstitial lung disease

Administrative details of the data analysis	
Substance(s)	Edoxaban, Apixaban, Rivaroxaban, Dabigatran
Condition/ADR(s)	Interstitial lung disease
Short title of topic	ILD and DOACs
Study team	[name], [name] and [name]

1. List of abbreviations

MAH	Marketing Authorisation Holder
EMA	European Medicines Agency
PRAC	Pharmacovigilance Risk Assessment Committee

2. Milestones

Milestone	Planned date
Draft analysis plan prepared	24/03/2023
Revised analysis plan following review	21/06/2023
Final analysis report	TBD

3. Rationale and background

Interstitial lung disease (ILD) describes a heterogenous group of respiratory disorders affecting the interstitium of the lungs. [1,2] ILD may occur when an injury to the lungs triggers an abnormal healing response. The repair process is disrupted, and the tissue around the alveoli becomes scarred and thickened. Prolonged ILD may result in pulmonary fibrosis, but this is not always the case. [1,2]

Cases of interstitial lung disease (ILD) have been recently described, especially in Asian subjects, in people using direct oral anticoagulants (DOACs) [3-5]. In addition, a recently published observational study suggests an increased risk of ILD in patients treated with factor Xa inhibitors (edoxaban, apixaban, rivaroxaban) as compared to warfarin users among subjects with non-valvular atrial fibrillation in Taiwan [6, 7], which triggered a new potential safety signal. A thorough review of this issue within the ongoing and upcoming PSUSA procedures for edoxaban, apixaban and rivaroxaban is expected. In this context, a real-world data (RWD) analysis has been requested to better inform the PRAC on the relationship between increased risk of ILD and use of DOACs in the European population.

4. Research question and objectives

Is the use of factor Xa (FXa) inhibitors (edoxaban, apixaban and rivaroxaban) or direct thrombin inhibitor (dabigatran) associated with an increased risk of interstitial lung disease (ILD) when compared with patients treated with vitamin K antagonists (VKA), among patients with Atrial Fibrillation (AF), Deep Vein Thrombosis (DVT) and Pulmonary Embolism (PE)?

5. Research methods

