5.3. Setting and study population

The included study population will consist of adult new users of the anticoagulants of interest (see section on Exposures), as recorded for patients visiting general practices (UK, Germany, Spain, and Italy). Patients will require to have been observed at least once at minimum one year (365 days) prior to entering the cohort. In the UK database, this will be defined as a minimum of 365 days between registration with the practice and the index date. For the other databases, this will be defined as a record of health care system use recorded in the databases at least 365 days prior to the index date.

The population will be stratified by indication for anticoagulation, namely for the management of atrial fibrillation (AF) or for the management of venous thromboembolism (VTE, namely deep vein thrombosis or pulmonary embolism). Indications will be identified by the presence of diagnosis codes within the individual's electronic health record in the year up to the index date. Patients initiating anticoagulation with no diagnostic code for AF or VTE will not be included in the analysis. For patients with multiple indications, the most recent indication (before index date) will be used. Patients with a history of cardiac mechanical valve or mitral stenosis prior to cohort entry will be excluded, as they have an indication for warfarin, not DOACs.

Individuals with a diagnosis of ILD prior to cohort entry (anytime in the patient's prior history) will be excluded from the cohort.

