Annex 2 – Code lists

- List of codes and terms that will be used for narrow and broad ILD definition:

ILD_broad and
narrow list_21.06.20

- List of codes and terms that will be used to identify DOACs and Vitamin K Antagonist:

DOACs - RxNorm
and RxNorm Extensi

VitKAntagonists_21.
06.2021.xlsx

- List of codes and terms that will be used to identify AF, DVT and PE patients:

Indications - 2023
08 03.xlsx

- List of codes and terms that will be used to identify exposure to co-medications:

DOAC-ILD-Covariat
e-Drugs_21.06.2023.

- List of codes and terms that will be used to identify comorbidities and smoking:

DOAC-ILD-Covariat
e-Codes 2023 08 03.

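### Within the VTE stratum, PE versus DVT is neither matched on nor a named propensity-score covariate, so a PE imbalance could bias the VTE hazard ratios without being seen

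*Protocol*

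**What the plan says.** The research question in section 4 names the three conditions one by one: "among patients with Atrial Fibrillation (AF), Deep Vein Thrombosis (DVT) and Pulmonary Embolism (PE"). Section 5.3 reduces them to two strata, AF and "venous thromboembolism (VTE, namely deep vein thrombosis or pulmonary embolism"). Section 5.6.2 matches within these two strata only: "Matching will occur by indication (AF and VTE").

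On the content of the score, section 5.6.2 states: "We will include the baseline risk factors and calendar year as predictor variables in the propensity score". The risk factors are those of section 5.5, which begins "Baseline risk factors for ILD will be measured including: age, sex, history of pneumonia, chronic obstructive pulmonary disease, chronic kidney disease, hepatitis C" and continues with further comorbidities, co-medications and smoking. Neither PE nor DVT is named there.

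Balance is judged on the standardised mean difference of each variable, "with SMD of less than 0.1 representing successful matching". Annex 2 contains a "List of codes and terms that will be used to identify AF, DVT and PE patients", so the data to tell PE from DVT are planned. Section 5.8 says that the analysis controls for confounders observed at baseline.

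**The concern.** The outcome is a recorded diagnosis, and its narrow definition includes pulmonary fibrosis and pneumonitis (section 5.5). PE is a lung event that usually brings respiratory symptoms and chest imaging; DVT alone does not. It is therefore plausible that ILD is found or coded more often after PE than after DVT. This is clinical reasoning, not a statement in the protocol. If DOAC and VKA starters also differ in their PE share, matching on the named variables need not remove that difference. Because SMDs are calculated for the variables in the plan, a PE imbalance would not appear in the balance table.

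The hazard ratios at stake are those of the VTE stratum. An imbalance there could produce an apparent ILD association or mask a real one. The caveat on residual confounding in section 5.8 concerns factors that cannot be included, unknown factors and time-varying factors. PE versus DVT is none of these: it is a baseline variable that the study plans to code.

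**Working it through.** **The plan's own count.** Section 5.6.2 gives 4 countries × 5 exposures × 2 indications = 40 analyses, which reproduces. The VTE stratum holds 4 × 5 × 1 = 20 of them. This is a count of analyses, not a share of the information.

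**Inputs from the protocol.** One VTE stratum for DVT and PE (section 5.3); two matching strata (section 5.6.2); a score from the section 5.5 list plus calendar year; an SMD limit of 0.1.

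**Inputs that must be assumed.** The protocol gives no PE shares by arm and no rate of recorded ILD after PE or DVT. Let p1 and p0 be the PE shares in the matched DOAC and VKA arms, and R the ratio of recorded ILD rates, PE to DVT.

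**Formulas.** For a rare outcome and one unbalanced binary covariate:

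- bias factor = observed HR / true HR = (p1·R + 1 − p1) / (p0·R + 1 − p0)
- SMD = |p1 − p0| / √[(p1(1 − p1) + p0(1 − p0)) / 2]

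**Worked cases.**

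- 45% vs 40%, R = 2: (0.90 + 0.55) / (0.80 + 0.60) = 1.45/1.40 = 1.036. SMD = 0.05/√0.24375 = 0.101.
- 50% vs 40%, R = 2: 1.50/1.40 = 1.071; R = 3: 2.00/1.80 = 1.111. SMD = 0.10/√0.245 = 0.202.

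| PE share DOAC / VKA | SMD | R = 1 | R = 1.5 | R = 2 | R = 3 |
|---|---|---|---|---|---|
| 40% / 40% | 0.00 | 1.00 | 1.00 | 1.00 | 1.00 |
| 45% / 40% | 0.10 | 1.00 | 1.02 | 1.04 | 1.06 |
| 40% / 45% | 0.10 | 1.00 | 0.98 | 0.97 | 0.95 |
| 50% / 40% | 0.20 | 1.00 | 1.04 | 1.07 | 1.11 |
| 40% / 50% | 0.20 | 1.00 | 0.96 | 0.93 | 0.90 |

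Three things follow. There is no bias if the shares are equal or if R = 1. The direction depends on which arm has more PE, which the documents do not say. An imbalance of ten percentage points has an SMD of about 0.20, twice the protocol's limit, so it would be flagged if PE were in the table and goes unseen if it is not. Holding PE to an SMD of about 0.1 limits the shift to roughly 6% for R up to 3.

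**The case against.** A reader might infer that the VTE estimate is confounded, through an indication that is known to change ILD detection. The documents do not support that. They show neither a different PE share between arms nor a higher rate of recorded ILD after PE, and both are needed.

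The detection argument is also weakened by the design. Most of the work-up for a PE comes before anticoagulation starts, and that start is the index date (section 5.4). Anyone with ILD recorded before entry is excluded (section 5.3), on the broad composite of ILD codes (section 5.5), so ILD coded during the work-up removes the patient. This stands, but only in part: no lag after the index date is stated, and the data are primary care records without hospital linkage (section 5.8), so a finding from the work-up may be coded only after entry.

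The score already contains variables that may correlate with PE, such as age, pneumonia, COPD, cancer and calendar year. They may balance part of a difference but do not guarantee it.

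The section 5.5 list is introduced as non-exhaustive and the Annex 2 covariate file is not visible, so the absence of PE is certain only for the named list.

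A reader might also take the research question to promise separate DVT and PE results. It does not: it describes the eligible population, and the pooling into VTE is declared and used consistently. Pooling as such is not an error.

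**Conclusion.** The point holds as a gap in adjustment and in the balance check, not as demonstrated bias. PE versus DVT is a planned baseline variable that is neither a matching factor nor a named score covariate, and the stated SMD checks would not reveal an imbalance in it. The VTE hazard ratios may be confounded in either direction. Under the assumed inputs the shift is 2% to 6% for a five-point difference in PE share with R from 1.5 to 3, and 7% to 11% upwards or 7% to 10% downwards for a ten-point difference with R from 2 to 3. With equal shares it is nil. These figures rest wholly on the assumed shares and rate ratios, on a rare outcome, and on PE being the only unbalanced factor.

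The reach is limited. Hazard ratios are reported by indication, so the AF results are not affected. The case for acting is that the check costs almost nothing.

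**What to change.** In section 5.6.2, add a baseline PE-versus-DVT indicator to the propensity score in the VTE stratum, or match exactly on it, and list it in the SMD table before and after matching. Use the same indicator in the score if the IPTW fallback or the calendar-stratified matching of section 5.6.6 is used.

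State how patients with both codes are classified, consistently with the section 5.3 rule that the most recent indication before the index date is used. That rule does not settle DVT and PE codes entered on the same date, so a tie-break is needed; assigning ties to PE is one option.

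Keep VTE as one stratum, which leaves the count at 40. Full separate strata would raise it to 4 × 5 × 3 = 60, in a study with no sample-size requirement (section 5.6.5). Report PE and DVT separately only as a sensitivity analysis where events allow.

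The cost is one variable from codes already planned. Adding it to the score costs essentially nothing; exact matching may lose a few pairs. If the covariate file already includes PE, one clarifying sentence in section 5.5 is enough.
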